5.5.2 Sponsor Follow-Up

For SAEs, adverse events of special interest, and pregnancies, the Sponsor or a designee may follow up by telephone, fax, electronic mail, and/or a monitoring visit to obtain additional case details and outcome information (e.g., from hospital discharge summaries, consultant reports, autopsy reports) in order to perform an independent medical assessment of the reported case.

5.6 ADVERSE EVENTS THAT OCCUR AFTER THE ADVERSE EVENT REPORTING PERIOD

After the end of the adverse event reporting period (defined as 90 days after the last dose of study treatment), all deaths, regardless of cause, should be reported through use of the Long-Term Survival Follow-Up eCRF.

In addition, if the investigator becomes aware of a serious adverse event that is believed to be related to prior exposure to study drug, the event should be reported through use of the Adverse Event eCRF.

An exception is made for Grade 3 and 4 infections (related and unrelated to prior study treatment), which should be reported until up to 2 years after the last dose of study treatment.

The Sponsor should also be notified of events of second malignancies indefinitely (related and unrelated to study treatment, even if the G+Atezo+pol treatment group or the overall study has been closed) for patients who received obinutuzumab.

If the EDC system is not available, the investigator should report these events directly to the Sponsor or its designee, either by faxing or by scanning and emailing the paper

Clinical Trial Serious Adverse Event/Adverse Event of Special Interest Reporting Form using the fax number or email address provided to investigators.

**5.7 EXPEDITED REPORTING TO HEALTH AUTHORITIES,
INVESTIGATORS, INSTITUTIONAL REVIEW BOARDS, AND
ETHICS COMMITTEES**

The Sponsor will promptly evaluate all SAEs and adverse events of special interest against cumulative product experience to identify and expeditiously communicate possible new safety findings to investigators, IRBs, ECs, and applicable health authorities based on applicable legislation.

To determine reporting requirements for single adverse event cases, the Sponsor will assess the expectedness of these events using the following reference document:

- Obinutuzumab Investigator's Brochure
- Atezolizumab Investigator's Brochure
- Polatuzumab Vedotin Investigator's Brochure
- Rituximab Investigator's Brochure

The Sponsor will compare the severity of each event and the cumulative event frequency reported for the study with the severity and frequency reported in the applicable reference document.

Reporting requirements will also be based on the investigator's assessment of causality and seriousness, with allowance for upgrading by the Sponsor as needed.

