2. OBJECTIVES AND ENDPOINTS

This study will evaluate the safety, efficacy, pharmacokinetics, and immunogenicity of induction treatment consisting of obinutuzumab in combination with atezolizumab plus polatuzumab vedotin (G+Atezo+Pola) in patients with relapsed or refractory FL and rituximab in combination with atezolizumab + polatuzumab vedotin (R+Atezo+Pola) in patients with relapsed or refractory DLBCL, followed by post-induction treatment with G+Atezo (referred to as maintenance) in patients with FL who achieve a CR, a PR, or stable disease at EOI and post-induction treatment with R+Atezo (referred to as consolidation) in patients with DLBCL who achieve a CR or PR at EOI (see Section 3.1 for details). Specific objectives and corresponding endpoints for the study are outlined below, in accordance to study changes from Protocol BO29561, Version 7.

In this study, "study treatment" refers to the combination of all study treatment components.

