5.1.2.2 Infections (Including Serious Infections)

Serious infections, including fatal bacterial, fungal, and new or reactivated viral infections, can occur during and up to 1 year following completion of rituximab-based therapy.

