5.3.1 Adverse Event Reporting Period

Investigators will seek information on adverse events at each patient contact. All adverse events, whether reported by the patient or noted by study personnel, will be recorded in the patient's medical record and on the Adverse Event eCRF.

After informed consent has been obtained **but prior to initiation of study treatment**, only SAEs caused by a protocol-mandated intervention (e.g., invasive procedures such as biopsies, discontinuation of medications) should be reported (see Section 5.4.2 for instructions for reporting SAEs).

After initiation of study treatment, all adverse events will be reported until 90 days after the last dose of study treatment. After this period, the investigator should report any SAEs that are believed to be related to prior study treatment (see Section 5.6).

An exception is made for Grade 3 or 4 infections (related and unrelated to study treatment), which should be reported until up to 2 years after the last dose of obinutuzumab (G+Atezo+ Pola treatment group).

Similarly, second malignancies (related and unrelated to study treatment) will be reported indefinitely (even if the study has been closed) for patients who received obinutuzumab (see Section 5.6).

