- w After informed consent has been obtained but prior to initiation of study treatment, only serious adverse events caused by a protocol-mandated intervention should be reported. After initiation of study treatment, all adverse events will be reported until 90 days after the last dose of study treatment. After this period, the Sponsor should be notified if the investigator becomes aware of any serious adverse event that is believed to be related to prior study treatment (see Section [5.6](#)). The investigator should follow each adverse event until the event has resolved to baseline grade or better, the event is assessed as stable by the investigator, the patient is lost to follow-up, or the patient withdraws consent. Every effort should be made to follow all serious adverse events considered to be related to any of the study treatment components or trial-related procedures until a final outcome can be reported.
- x The screening PET-CT scan must be performed within 35 days prior to Day 1 of Cycle 1.
- y Perform only for patients who have received at least two cycles of induction treatment.

Appendix 2

Schedule of Assessments for Patients with Diffuse Large B-Cell Lymphoma (cont.)

- ^z Includes CT scan of the neck (if clinically indicated), chest, abdomen, and pelvis. If contrast is medically contraindicated (e.g., patients with contrast allergy or impaired renal clearance), MRI scans of the chest, abdomen, and pelvis (and neck, if clinically indicated) and a non-contrast CT scan of the chest may be performed. Combined PET/CT scanners may be used to collect diagnostic CT scans, but only according to the technical guidelines in the imaging manual. The screening CT scan must be performed within 35 days prior to Day 1 of Cycle 1.
- ^{aa} Perform within 7 days prior to Day 1 of Cycle 3. Patients with radiographic evidence of progression at the end of Cycle 2 who continue to receive study treatment per criteria defined in Section 3.1.1 should have a CT scan repeated 4–8 weeks later.
- ^{bb} Bone marrow biopsy and aspirate must be performed within approximately 3 months prior to Day 1 of Cycle 1.
- ^{cc} For patients with bone marrow involvement at screening, a repeat assessment will be performed at EOI if there is radiologic evidence of a complete response or if clinically indicated (e.g., if there is clinical suspicion of progressive disease in the bone marrow with no radiologic evidence of progression).

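### Sections 5.3.1 and 5.6 disagree on whether non-fatal Grade 3–4 infections that are non-serious or judged unrelated are reportable after day 90 in the 23 DLBCL patients

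*Combined protocol and SAP*

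**What the plan says.** The general rule in Section 5.3.1 is that "all adverse events will be reported until 90 days after the last dose of study treatment"; after that, only serious events believed related to prior study treatment are reported. The section then makes an exception for Grade 3 or 4 infections, related and unrelated, "which should be reported until up to 2 years after the last dose of obinutuzumab", and names the G+Atezo+Pola group in parentheses.

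Section 5.6, which governs events after the reporting period, states the exception differently. Grade 3 and 4 infections, again whatever their relationship to treatment, are events "which should be reported until up to 2 years after the last dose of study treatment". No drug or group is named. Section 2 says that study treatment "refers to the combination of all study treatment components".

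The schedules of assessments follow Section 5.3.1. Appendix 1 footnote aa (FL) carries the exception, tied to obinutuzumab. Appendix 2 footnote w (DLBCL) says "After initiation of study treatment, all adverse events will be reported until 90 days after the last dose of study treatment", then mentions only related serious events and points to Section 5.6. It has no infection exception.

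On analysis, Section 5.2.5 makes all infections selected adverse events. Section 6.5 has selected adverse events summarized and listed by treatment group, with the main safety analysis using data to end of study.

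**The concern.** DLBCL patients receive rituximab and polatuzumab vedotin, never obinutuzumab. Under Section 5.3.1 and Appendix 2 the extended infection window does not reach them. Under Section 5.6, read as written, it does. These are two operative collection rules in the same protocol version, and a site could follow either one and believe that it complies.

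The period in question is one in which the protocol itself expects risk: Section 5.1.2.2 says that serious infections "can occur during and up to 1 year following completion of rituximab-based therapy". Because the main safety summary runs to end of study and Section 6.5 sets no common infection window, events after day 90 enter the main tables. If sites read the rule differently, the DLBCL count of late Grade 3–4 infections would mix patients observed under different rules, and the table would not show which.

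**Working it through.** The plan gives no figure to reproduce. The check sets the four statements side by side, identifies which events depend on the choice between them, and then sizes the gap.

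**1. The four statements**

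| Place | Rule for Grade 3–4 infections | Clock starts | Scope |
|---|---|---|---|
| Section 5.3.1 | up to 2 years | last dose of obinutuzumab | G+Atezo+Pola group |
| Appendix 1, footnote aa | up to 2 years | last dose of obinutuzumab | FL schedule |
| Appendix 2, footnote w | no exception; 90 days, then related serious events, with a reference to Section 5.6 | last dose of study treatment | DLBCL schedule |
| Section 5.6 | up to 2 years | last dose of study treatment | none stated |

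**2. Can Section 5.6 be read as silently limited to obinutuzumab?** Its next paragraph, on second malignancies, carries an explicit limit: "even if the G+Atezo+pol treatment group or the overall study has been closed) for patients who received obinutuzumab". The authors restricted scope there when they meant to, so the unrestricted infection sentence cannot be assumed to carry the same limit.

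**3. Which DLBCL events after day 90 depend on the choice?**

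- Serious and believed related: reportable under every version.
- Death from any cause: reportable under Section 5.6, which nothing elsewhere contradicts.
- Non-fatal Grade 3–4, serious but judged unrelated: reportable under Section 5.6, not under Section 5.3.1 or Appendix 2.
- Non-fatal Grade 3–4, non-serious, whether related or not: reportable under Section 5.6, not under Section 5.3.1 or Appendix 2.

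Only the last two classes are at stake.

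**4. Size.** Enrolment in Section 6.1 is 13 FL and 23 DLBCL. The share affected is 23 / (13 + 23) = 23 / 36 = 63.9%. The nominal windows are 90 days and 2 × 365 = 730 days, a gap of 730 − 90 = 640 days.

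**5. Can 2 years be realised?** Section 3.2 ends the study when all patients have completed the 90-day safety visit. Appendix 2 footnote ee ends it when all FL patients have finished or stopped treatment and all DLBCL patients have been followed for at least 1 year. Neither guarantees 2 years. If a DLBCL patient were followed for exactly 1 year, the disputed period would be 365 − 90 = 275 days.

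**6. The FL group.** The scope agrees across sections, but the clock does not: last dose of obinutuzumab in one place, last dose of study treatment in the other. Section 4.6.2 allows one drug to stop while others continue, so the two dates can differ.

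**The case against.** The strongest reply is that intent is clear. Section 5.3.1 and both appendices point to an obinutuzumab-only exception, and Section 5.6 is the outlier. Section 5.6 does not say that it covers all patients; that reading is inferred from its unrestricted wording and the definition of study treatment. This carries weight as evidence of intent, but it does not remove the conflict: Section 5.3.1 and Appendix 2 footnote w both send the reader to Section 5.6 for events after the reporting period.

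A second reply is that the risk in Section 5.1.2.2 concerns serious infections, and those believed related are captured after day 90 under any reading, as are all deaths. That stands, and it confines the point to the two event classes identified in the working.

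A third is that Section 6.5 already uses a 90-day limit. It does so only in the sensitivity analysis, and as a calendar cut at 1 March 2018 plus 90 days, not as last dose plus 90 days. The main analysis has no such limit.

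A fourth is timing. Section 3.1.4 says that patients no longer receive atezolizumab or polatuzumab, and DLBCL consolidation has been removed. DLBCL treatment therefore appears to be over, and an amendment can affect only the follow-up that remains. That also stands, and it lowers the value of the wording change. It does not lower the value of the common-window table.

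A reader might go further and infer that sites do in fact report differently. The documents show that divergence is possible, not that it has happened.

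**Conclusion.** The contradiction is in the current text and should be reconciled. It is minor. It affects 23 of 36 patients (63.9%), and only their non-fatal Grade 3–4 infections after day 90 that are non-serious or judged unrelated. For those events the nominal limit is 90 days or up to 2 years. The documents do not settle which scope is intended.

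Two stronger readings are tempting and not supported. One is that DLBCL patients have an eight-fold difference in observation: 730 / 90 = 8.1 compares nominal limits and assumes survival and follow-up for the full 2 years, which neither end-of-study definition secures. At 1 year the ratio would be 365 / 90 = 4.1, and 90 days is not a complete stop because related serious events continue to be reported. The other is that late DLBCL infection data become uninterpretable. Section 6.5 is descriptive, plans no formal comparison of late infections, and much of the serious late risk is captured under either rule. What follows is that late counts could be unevenly ascertained between sites.

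The conclusion rests on reading Section 5.6 as written, with study treatment meaning all components. The documents give no rate of Grade 3–4 infection after day 90 for this regimen, so the number of events affected cannot be estimated.

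**What to change.** Reconcile Section 5.3.1, Section 5.6 and Appendix 2 footnote w so that they state one scope for the extended infection window (whether or not it includes rituximab-treated DLBCL patients) and one starting point for the clock. Align Appendix 1 footnote aa with the same starting point. Check the chosen length against a single end-of-study definition, since Section 3.2 and Appendix 2 footnote ee currently differ.

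In Section 6.5, tabulate Grade 3–4 infections up to 90 days after the last dose as the common window for both groups, and list later events separately with the time since last dose. This keeps the summary on equal footing even if reporting has already diverged.

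The cost is a few lines of amendment wording, one extra table, and possibly slightly more reporting for DLBCL sites. Events already missed may not be recoverable.

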6. STATISTICAL CONSIDERATIONS AND ANALYSIS PLAN

The study will include an initial dose-escalation phase followed by an expansion phase in relapsed or refractory FL patients; and a safety run-in phase followed by an expansion phase in relapsed or refractory DLBCL patients. The dose-escalation phase is designed to determine the RP2D for polatuzumab vedotin when combined with fixed doses of obinutuzumab and atezolizumab in patients with relapsed or refractory FL. During the expansion phase, patients with relapsed or refractory FL will undergo treatment with polatuzumab vedotin at the RP2D, obinutuzumab, and atezolizumab; and patients with relapsed or refractory DLBCL will undergo treatment with polatuzumab vedotin 1.8 or 1.4 mg/kg, rituximab, and atezolizumab.

Study data will be summarized separately for each phase. Data from the dose-escalation phase will be summarized by each polatuzumab vedotin dose cohort. Data from the expansion phase will be summarized by histologic subtype (i.e., FL or DLBCL).

6.1 DETERMINATION OF SAMPLE SIZE

Limited dose-finding will be conducted during the dose-escalation phase of polatuzumab vedotin in combination with obinutuzumab and atezolizumab. The estimated sample size follows from the dose-escalation rules for a standard 3+3 algorithm, as outlined in Section 3.1.

A total of 9 patients with RR FL were enrolled in the dose-escalation phase (3 patients in the Pola 1.4-mg dose cohort and 6 patients in the Pola 1.8-mg dose cohort), and a total of 7 patients with RR DLBCL were enrolled into the safety run-in phase and treated with 1.8 mg polatuzumab vedotin. During the expansion phase, 34–40 patients with DLBCL and 34–37 patients with FL (for a total of 40 patients with FL at RP2D in the dose-escalation and expansion phases) were planned to be enrolled. Overall, approximately 83–92 patients were planned to be enrolled in the study. As of 1 March 2018, 13 patients with RR FL and 23 patients with RR DLBCL were enrolled in the study.

The primary efficacy analysis will be the estimation of the true proportion of patients expected to obtain a PET-CT–defined CR at EOI.

6.2 DEFINITION OF ANALYSIS POPULATIONS

For both the safety and efficacy analyses, the following populations are defined:

- The primary population will include patients who received at least 1 dose of each component of the combination.
- The intent-to-treat population will include all patients enrolled in the study.

Patients with FL who receive polatuzumab vedotin at the RP2D during the dose-escalation phase will be pooled with patients who receive polatuzumab vedotin at the RP2D during the expansion phase.

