3.1.2.1.2 Treatment Regimens and Dose-Escalation Rules

A 3+3 dose-escalation schema was used. Induction treatment was administered in 21-day cycles, as outlined in [Table 1](#). Obinutuzumab and atezolizumab will remain at fixed doses during the dose-escalation phase. For polatuzumab vedotin, there are two possible dose levels: 1.4 or 1.8 mg/kg. If the starting dose of 1.4 mg/kg is safe and tolerable, the polatuzumab vedotin dose will be escalated to 1.8 mg/kg. Intrapatient dose escalation is not allowed.

Table 1 Induction Treatment for Dose-Escalation Phase

Cycle	G + Atezo + Pola (21-Day Cycles)
1	Obinutuzumab 1000 mg IV on Days 1, 8, and 15 Polatuzumab vedotin 1.4 mg/kg or 1.8 mg/kg IV on Day 1
2–6	Obinutuzumab 1000 mg IV on Day 1 Atezolizumab 1200 mg IV on Day 1 Polatuzumab vedotin 1.4 mg/kg or 1.8 mg/kg IV on Day 1

IV=intravenous.

Dose escalation occurred in accordance with the rules listed below:

First Dosing Group (Polatuzumab Vedotin 1.4 mg/kg)

- A minimum of 3 patients will initially be sequentially enrolled in the first dosing group (polatuzumab vedotin 1.4 mg/kg). The 3 patients will be enrolled at least 24 hours apart.
- If none of the first 3 DLT-evaluable patients experiences a DLT, enrollment of the second dosing group (i.e., polatuzumab vedotin 1.8 mg/kg) may proceed.
- If 1 of the first 3 DLT-evaluable patients experiences a DLT, the dosing group will be expanded to at least 6 patients. If there are no further DLTs in the first 6 DLT-evaluable patients, enrollment of the second dosing group may proceed.
- If 2 or more of the first 3–6 DLT-evaluable patients experience a DLT, the RP2D will have been exceeded, and dose escalation will stop and study will be discontinued.

Second Dosing Group (Polatuzumab Vedotin 1.8 mg/kg)

- A minimum of 3 patients will initially be enrolled sequentially in the second dosing group (polatuzumab vedotin 1.8 mg/kg). The 3 patients will be enrolled at least 24 hours apart.
- If none or 1 of the first 3 DLT-evaluable patients experiences a DLT, the dosing group will be expanded to at least 6 patients. If there are no further DLTs, 1.8 mg/kg will be declared the RP2D for polatuzumab vedotin.

- If 2 or more of the first 3–6 DLT-evaluable patients experience a DLT, the RP2D will have been exceeded, and 1.4 mg/kg will be declared the RP2D for polatuzumab vedotin.

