In Study PCD4989g, atezolizumab was safely administered to 11 patients with various hematologic malignancies (including 7 patients with lymphoma) at doses of 15 mg/kg Q3W (n=1) or 20 mg/kg Q3W (n=10). Atezolizumab 1200 mg Q3W is currently being evaluated in combination with obinutuzumab in an ongoing Phase Ib study (Study GO29383) in patients with relapsed or refractory DLBCL or FL (see Section 1.3.2). Atezolizumab was added to obinutuzumab/rituximab starting with Cycle 2 to avoid overlapping IRRs during the first infusion of obinutuzumab, which is known to be associated with the highest incidence and risk of severe IRRs. Consistent with the dosing schedule used in Study GO29383, in this study, atezolizumab was added to G/R+Pola starting with Cycle 2.

As of Protocol BO29561, Version 7, dosing with atezolizumab is discontinued in all patients still receiving study treatment.

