6.6 EFFICACY ANALYSES

The primary and secondary efficacy analyses will include all patients enrolled in the expansion phase, and will be performed by treatment group. In addition, patients with FL who received polatuzumab vedotin at the RP2D during the dose-escalation phase will be pooled for analysis with patients with FL treated in the expansion phase. Patients with DLBCL from the safety run-in phase will be pooled for analysis with patients with DLBCL treated in the expansion phase at the same polatuzumab vedotin dose. A censoring will be applied as of 1 March 2018 to the efficacy analyses, to evaluate the effect of the triplet drug combination in each treatment group. The efficacy analysis will be performed on the censored efficacy dataset, and will include data from patients as of 1 March 2018 plus the corresponding assessment time window (see [Appendix 1](#) and [Appendix 2](#)).

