6.6.1 Primary Efficacy Endpoint

The primary efficacy analysis will be estimation of the proportion of patients achieving a CR at EOI, as determined by the investigator through use of the PET-CT-based Lugano 2014 criteria (see [Appendix 5](#)). Point estimates will be presented, along with the

corresponding two-sided 90% Clopper-Pearson exact CIs. Patients without a post-baseline tumor assessment will be considered non-responders.

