- t Includes B-cell counts (CD19), T-cell counts (CD3, CD4, and CD8), and NK cell counts (CD16 and CD56).
- u Cycles 2 and 3 only.
- v Perform at the same time as tumor assessments at 12 and 18 months after initiation of induction treatment.
- w Requires separate patient consent for RCR participation. Not applicable for a site that has not been granted approval for RCR sampling.
- x Availability of adequate archival or freshly biopsied tumor tissue samples should be confirmed at screening (see Section [4.5.7](#) for details).
- y A tumor biopsy sample will be collected prior to the start of Cycle 2 and at the time of progression unless no adequate tumor site is accessible.
- z Includes any medication (e.g., prescription drugs, over-the-counter drugs, herbal or homeopathic remedies, nutritional supplements) used by a patient from 7 days prior to the screening period until the EOI or EOM visit, whichever occurs later.
- aa After informed consent has been obtained but prior to initiation of study treatment, only serious adverse events caused by a protocol-mandated intervention should be reported. After initiation of study treatment, all adverse events will be reported until 90 days after the last dose of study treatment. After this period, the Sponsor should be notified if the investigator becomes aware of any serious adverse event that is believed to be related to prior study treatment (see Section [5.6](#)). An exception is made for Grade 3 or 4 infections (related and unrelated), which should be reported until up to 2 years after the last dose of obinutuzumab. The investigator should follow each adverse event until the event has resolved to baseline grade or better, the event is assessed as stable by the investigator, the patient is lost to follow-up, or the patient withdraws consent. Every effort should be made to follow all serious adverse events considered to be related to any of the study treatment components or trial-related procedures until a final outcome can be reported.
- bb The screening PET-CT scan must be performed within 35 days prior to Day 1 of Cycle 1.
- cc Perform only for patients who have received at least two cycles of induction treatment.
- dd If PET-CT scan is positive at EOI, perform at 12 months after initiation of induction treatment, within 14 days prior to treatment administration.

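### Sections 6.2 and 6.6 give different denominators for CR at end of induction, neither is assigned to the endpoint, and the 6.2 set can drop early failures

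*Combined protocol and SAP*

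**What the plan says.** Section 6.2 defines two populations and says that both serve safety and efficacy. The first is labelled primary: "The primary population will include patients who received at least 1 dose of each component of the combination". The second is wider: "The intent-to-treat population will include all patients enrolled in the study". Neither is tied to an endpoint.

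Section 6.6 describes the efficacy analyses differently: "The primary and secondary efficacy analyses will include all patients enrolled in the expansion phase". It adds the FL patients treated at the RP2D in dose escalation and the DLBCL run-in patients at the same polatuzumab vedotin dose. It sets no dosing condition and names neither 6.2 population. The synopsis repeats this inclusion and pooling. Section 6.6 also applies a cut-off, so that the efficacy dataset "will include data from patients as of 1 March 2018 plus the corresponding assessment time window".

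Section 6.6.1 names no population. Its rule for missing assessments is: "Patients without a post-baseline tumor assessment will be considered non-responders".

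Three facts on timing matter:
- Table 1 (Section 3.1.2.1.2) lists "Atezolizumab 1200 mg IV on Day 1" for Cycles 2–6 and not for Cycle 1. Section 3.3.2.2 confirms it for both treatment groups: "Atezolizumab was added to obinutuzumab/rituximab starting with Cycle 2".
- The EOI PET-CT carries this footnote in Appendix 1 (FL) and Appendix 2 (DLBCL): "Perform only for patients who have received at least two cycles of induction treatment".
- The first scheduled CT after baseline falls within 7 days before Day 1 of Cycle 3 (same appendices).

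**The concern.** In a single-arm study whose efficacy aim is to estimate a proportion, the denominator is part of what is being estimated. Here two sections give different denominators for the primary endpoint and nothing ranks them.

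The difference is related to outcome. Entry to the 6.2 set requires a drug that is first given three weeks into treatment. A patient who stops before that dose because of death, progression or toxicity is outside the 6.2 set, but inside the 6.6 set as a non-CR. Dropping such patients can only raise the CR rate. At stake is the reported rate and its interval.

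**Working it through.** **Inputs.** Section 6.1 gives 13 FL patients enrolled (9 in escalation: 3 at 1.4 mg/kg and 6 at 1.8 mg/kg) and 23 DLBCL patients (7 in the run-in). Section 6.6.1 sets two-sided 90% Clopper-Pearson intervals. The plan gives neither the number never dosed with atezolizumab nor the number of CRs, so both are assumed below.

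**The plan's own pooling figure.** Section 6.1 plans 40 FL patients at the RP2D with 34–37 in expansion. That reproduces as 6 + 34 = 40 or 3 + 37 = 40, so the FL efficacy set is escalation at the RP2D plus expansion.

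**Actual size of the 6.6 sets.**
- FL: 13 − 3 = 10, that is 6 escalation + (13 − 9) = 4 expansion.
- DLBCL: 23, that is 7 run-in + (23 − 7) = 16 expansion, all taken to be at 1.8 mg/kg.

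The intent-to-treat set, read literally, has 13 FL patients because it includes the three at 1.4 mg/kg. It therefore does not match 6.6 either.

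**Patients who stop before Cycle 2.** They have had fewer than two cycles, get no EOI PET-CT and cannot be CRs. Let x be the CRs, N the size of the 6.6 set and k the number of such patients. The 6.6 rate is x/N, the 6.2 rate is x/(N − k), and their ratio is N/(N − k).

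| Group | Assumed CRs | k | Rate (90% CI) | Factor |
|---|---|---|---|---|
| DLBCL | 8 | 0 | 8/23 = 34.8% (18.6–54.0) | 1.00 |
| DLBCL | 8 | 1 | 8/22 = 36.4% (19.6–56.1) | 1.05 |
| DLBCL | 8 | 2 | 8/21 = 38.1% (20.6–58.3) | 1.10 |
| DLBCL | 4 | 0 | 4/23 = 17.4% (6.2–35.5) | 1.00 |
| DLBCL | 4 | 2 | 4/21 = 19.0% (6.8–38.4) | 1.10 |
| DLBCL | 12 | 0 | 12/23 = 52.2% (33.5–70.4) | 1.00 |
| DLBCL | 12 | 2 | 12/21 = 57.1% (37.2–75.5) | 1.10 |
| FL | 5 | 0 | 5/10 = 50.0% (22.2–77.8) | 1.00 |
| FL | 5 | 1 | 5/9 = 55.6% (25.1–83.1) | 1.11 |

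**Limit on k for FL.** Section 4.6.2 replaces any escalation patient who leaves the DLT window (Cycles 1 and 2) for a reason other than a DLT. The 1.8 mg/kg group had to reach at least 6; exactly 6 were enrolled and Section 3.1.2.1 reports no DLT. If the rule was followed, none of those 6 stopped before Cycle 2, and k can come only from the 4 expansion patients. The replacement rule is worded for dose escalation, so it gives no such bound for the DLBCL run-in.

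**Patients who missed atezolizumab for other reasons.** If m patients are excluded and r of them are CRs, the 6.2 rate is (x − r)/(N − m). This exceeds x/N only when r/m < x/N. With 8 CRs in 23 DLBCL patients, m = 2 and r = 1, it falls to 7/21 = 33.3% (16.8–53.6).

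**How the cut-off treats them.** A patient who missed atezolizumab through the stop has Cycle 2 Day 1 on or after 1 March 2018. With 21-day cycles, Cycle 6 Day 1 is at least 84 days later (24 May 2018). EOI, 6–8 weeks after that, is on or after 5 to 19 July 2018 (+126 to +140 days). Even an assessment window read as a full 8 weeks ends on 26 April 2018. The EOI scan of such a patient who completes six cycles is therefore outside the efficacy dataset, and under 6.6 the patient could be counted as a non-responder.

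**The case against.** The best defence is that 6.2 settles the matter. It applies expressly to efficacy and labels one set primary. Section 4.6.2 uses the same criterion to decide which expansion patients are replaced. On this view 6.6 merely says which phases and doses are pooled. A set that requires every component is also a defensible choice when the question is the effect of the triplet. This is plausible but not conclusive: 6.6 speaks of all patients enrolled. The non-responder rule in 6.6.1 also fits the wider set better, since with the first scheduled CT just before Cycle 3 the patients it would mainly catch are those whom 6.2 removes.

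A reader might infer three stronger things that the documents do not support.

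- *That every Cycle 1 failure is lost under 6.2.* Only patients who stop before the first atezolizumab dose are lost. Progression in Cycle 1 that goes undetected leaves the patient on treatment, dosed in Cycle 2 and in the 6.2 set.
- *That the CR rate will be inflated.* If 6.6 governs, these patients stay in the denominator. If 6.2 governs, it also excludes patients who missed atezolizumab because of the 1 March 2018 stop or, more narrowly, because one drug was dropped while the others continued (Section 4.6.2). They could respond. Section 6.5 anticipates patients never given atezolizumab, but sets them apart for safety only.
- *That 6.6 as written is free of bias.* The cut-off could turn stop-affected patients into non-responders and lower the rate.

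It also stands that the effect is modest and that Section 6.3 lists discontinuations and dosing. From these a reader could partly reconstruct k, but not which denominator was intended.

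**Conclusion.** The inconsistency is in the current text, it concerns the primary endpoint, and it should be fixed. If 6.2 is followed, patients who stop before Cycle 2 through death, progression or toxicity are removed although they cannot be CRs, which by itself raises the rate by N/(N − k). The net direction is assured to be upward only if every excluded patient is a non-CR.

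The illustrated upward shifts are about 2 to 6 percentage points, with widely overlapping intervals. They rest on assumed k and CR counts, on all 23 DLBCL patients being at 1.8 mg/kg, and on nobody having missed atezolizumab solely through the stop. The documents do not show that k exceeds zero. No hypothesis or threshold is attached to CR, so no test result changes. What is at risk is the reported rate and the reader's ability to tell which denominator was planned.

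**What to change.** - State in 6.2 and 6.6.1 that the primary denominator for CR at EOI is the pooled set described in 6.6.
- State that patients who stop before atezolizumab for progression, toxicity, death or withdrawal and have no EOI PET-CT count as non-responders. The present rule turns on having no post-baseline assessment, so it misses a Cycle 1 progressor who had the unscheduled scan that Section 4.5.6 requires when progression is suspected.
- Report the 6.2 set as a sensitivity analysis, with the number excluded and the reasons.
- List separately the patients who missed atezolizumab solely because of the 1 March 2018 stop, and state how the efficacy cut-off applies to them so that they do not become non-responders by default.

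The cost is wording in 6.2, 6.6 and 6.6.1 and one extra table; no new data are needed. The CR rate will be slightly less favourable than under 6.2 if k > 0.
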